4.3 Secondary Efficacy Endpoints

- The duration of any stable platelet response
- Proportion of subjects in whom a reduction in the dose of concomitant ITP therapy can be achieved while maintaining an adequate platelet count

4.4 Safety Endpoints

Safety endpoints include the frequency and severity of bleeding according to the IBL5; change from baseline (baseline value is the value at the initiation of active therapy) in blood pressure, liver function, and ANC; the incidence and severity of gastrointestinal (GI) effects (nausea, vomiting, diarrhea, abdominal pain); infection; and overall AEs.

4.5 Pharmacokinetic Endpoints

[figure not shown]
Characterization of the PK profile of R406 (the active metabolite of fostamatinib) including C_{max} , AUC, and T_{max} in a subset of subjects with ITP.

5.0 STUDY DESIGN

5.1 Summary of Study Description

This is a Phase 3 multicenter, open-label extension study to evaluate the long-term safety and the efficacy of fostamatinib in achieving and maintaining a stable platelet response in subjects with persistent/chronic ITP. For the purpose of this study, the term ‘subject’ will refer to patients with persistent/chronic ITP participating in this study. Up to 150 subjects will be enrolled at multiple sites. The study will consist of monthly visits for 18 months followed by every-other-month visits for a maximum of 5 years of treatment or until commercial availability of drug, whichever comes first (Figure 1).

Figure 1: Study Design

*At the end of Month 1 subjects receiving fostamatinib 100 mg *bid* should have the dose escalated to fostamatinib 150 mg *bid* if the platelet count is < 50,000/μL.

Eligible subjects include subjects from Study C-935788-047 or C-935788-048 who have completed the Week 24 evaluation or who discontinue early (starting at Week 12) due to lack of response. Subjects must meet the Inclusion/Exclusion criteria listed in [Section 6.1](#) and [Section 6.2](#) to be eligible to participate in the study. All subjects will receive open-label fostamatinib. Subjects designated as responders (defined as platelet count $\geq 50,000/\mu\text{L}$) at the time of rollover will continue in the extension study at their current Study C-935788-047 or C-935788-048 dose and regimen. Subjects who enter the extension study as nonresponders (defined as platelet count $< 50,000/\mu\text{L}$) will be allocated to fostamatinib 100 mg PO *bid* regardless of their dose and regimen in the prior study. Subjects will remain blinded to their treatment assignment from Study C-935788-047 or C-935788-048 (active or placebo).

Subjects may continue to receive the concomitant medications for ITP that were allowed in the prior study (ie, glucocorticoids at a dose less than the equivalent of 20 mg prednisone daily, azathioprine or danazol). Subjects in whom the platelet count is stable at $\geq 50,000/\mu\text{L}$ may have the dose of concomitant medications for ITP gradually reduced according to standard practice.

At the end of Month 1 (approximately Day 30), subjects receiving fostamatinib 100 mg PO *bid* should have the dose escalated to fostamatinib 150 mg PO *bid* if platelet count $< 50,000/\mu\text{L}$ and the study drug is well tolerated (refer to [Section 7.2.1](#)). Conversely, the dose may be reduced at any time to a dose as low as fostamatinib 100 mg PO *qd* if dose-limiting AEs are observed as

defined by this protocol (see Section 7.2.2 and Appendix 1, Appendix 2, Appendix 3, and Appendix 4).

5.2 Rationale for Proposed Dosing

Biomarker data from early studies of R940406 (R406), the active moiety of fostamatinib disodium, have demonstrated that the EC₅₀ for its pharmacodynamic effects on the syk pathway was 496 ± 42.2 ng/mL (~1.06 μM), roughly equivalent to a daily AUC of ~ 12,000 ng•h/mL.

Phase 2 and 3 studies of fostamatinib in rheumatoid arthritis (RA), evaluated multiple dose levels including 50 mg PO *bid*, 100 mg PO *bid* and 150 mg PO *qd* or *bid*. Doses of 100 mg to 150 mg PO *bid* were effective in ameliorating the signs and symptoms of RA, while 50 mg PO *bid* was not effective. The average R406 exposure at 100 mg PO *bid* ranged from 4,400 to 7,020 ng•h/mL per dose interval, with daily exposures ranging from 8,800 to 14,000 ng•h/mL. These exposures are consistent with the levels needed to affect the syk pathway, as defined in biomarker assays, and support the 100 mg PO *bid* starting dose for this study.

Additionally, fostamatinib was previously studied in a small pilot trial of patients with ITP. Platelet counts improved in the majority of treated subjects, typically at doses ranging from 100-150 mg PO *bid*.

[figure not shown]
The purpose of this study is to confirm the long-term safety of fostamatinib and the beneficial effects on platelet counts in patients with persistent/chronic ITP.

5.3 Study Treatment

Depending on their response to treatment in Study C-935788-047 or C-935788-048 there will be two categories of subjects in this study: responders and nonresponders (see Figure 2).

- Responders will initiate open-label fostamatinib treatment with the dose and regimen that was efficacious in achieving a stable platelet response in Study C-935788-047 or C-935788-048.
- Nonresponders will initiate treatment with fostamatinib 100 mg PO *bid*. If a nonresponding subject has previously required a dose reduction (to less than 100 mg PO *bid*) due to an AE, the Sponsor's Medical Monitor should be contacted regarding the subject's eligibility and the appropriate starting dose.

Figure 2: Initial Treatment Allocation

Subjects will self-administer the study drug throughout the 60-month treatment period. Subjects on a *bid* dosing regimen will self-administer 1 tablet once in the morning and once in the evening at least 8 hours apart. Subjects on a *qd* dosing regimen will self-administer 1 tablet per day by mouth in the morning.

At the end of Month 1 (approximately Day 30), subjects receiving fostamatinib 100 mg PO *bid* should have the dose escalated to fostamatinib 150 mg PO *bid* if platelet count < 50,000/ μ L and the study drug is well tolerated (refer to [Section 7.2.1](#)).

Subjects whose platelet count is consistently < 50,000/ μ L following 3 months (12 weeks) of treatment, and at least 4 weeks at a dose of 150 mg PO *bid* (provided this higher dose was tolerated), should be discontinued from the study, unless tangible clinical benefit for the use of fostamatinib is evident and the Sponsor agrees (all instances must be reviewed with the Sponsor's Medical Monitor). Examples of tangible clinical benefit may include, but are not limited to:

- Credible increase in platelet count (eg, increase in platelet count of at least 20,000/ μ L over initial baseline to a count \geq 30,000/ μ L)
- Reduction in bleeding
- Reduction in the need for rescue therapy

5.3.1 IWRS

An Interactive Web Response System (IWRS) will be used to dispense the appropriate dose of fostamatinib to subjects in the study. The IWRS will assign a bottle number to each subject who is eligible for the open-label extension study.

5.4 Safety Monitoring

The Rigel Medical Monitor and representatives will closely monitor the safety of study drug on an ongoing basis by assessing reported AEs, vital signs, clinical laboratory values (hematology, serum chemistry, and urinalysis), and physical exams.

5.5 Safety Review Committee

An independent safety review committee (SRC) will also monitor safety throughout the study.

5.6 Administrative Structure

This trial is sponsored by Rigel. Up to 150 subjects will be enrolled at multiple sites.

A contract research organization (CRO) will be responsible for project management and team training, site identification and activation, site monitoring and management, data management, randomization code assignment, and writing and preparation of the final clinical study report. A second vendor will be responsible for biometrics. An additional CRO will be responsible for electronic trial master file preparation and maintenance. A financial services vendor will be used for clinical site contract negotiation and site payments, and collection of financial disclosure information. A safety CRO will be responsible for safety database set-up, data entry and maintenance, coding of SAE data and SAE case processing and preparation of expedited safety reports.

Data will be recorded directly in an electronic case report form (eCRF) via an electronic data capture (EDC) system. An IWRS will be used for study drug inventory management. Counting of platelets will be performed at the investigational institution or by local laboratories affiliated with the clinical sites enrolling subjects in the study. A central laboratory will be used for testing other routine laboratory parameters as well as biospecimen storage (see [Section 7.6.6](#) for additional instruction).

6.0 SUBJECT SELECTION

6.1 Inclusion Criteria

1. Subject must be willing and able to give written informed consent by signing an IRB-approved Informed Consent Form prior to participating in any study-specific procedures.
2. Subjects must have completed the Week 24 evaluation of Study C-935788-047 or C-935788-048 or have discontinued early (starting at Week 12) due to lack of response. No more than 7 days may have elapsed between the last day of treatment on the Study C-935788-047 or C-935788-048 and initial dosing (Day 1) in Study C-935788-049.
3. Male or female at least 18 years of age.
4. Females must be either postmenopausal for at least 1 year or surgically sterile; or if female of child-bearing potential, must not be pregnant or lactating and must agree to use an acceptable method of birth control throughout the duration of the trial and for 30 days following the last dose. Acceptable methods of birth control are defined as: hormonal contraception (pill, injection or implant) used consistently for at least 30 days prior to enrollment, intrauterine device (IUD), double-barrier (ie, condom and spermicide, or condom and diaphragm), or complete abstinence.
5. In the Investigator's opinion, the subject has the ability to understand the nature of the study and any hazards of participation and to communicate satisfactorily with the Investigator.

6.2 Exclusion Criteria

1. Any subject who discontinued participation in Study C-935788-047 or C-935788-048 prior to Week 12 or for any reason other than lack of response. Exceptions may be considered on a case-by-case basis after consultation between the Investigator and Sponsor with the specific reason for the exception noted.
2. Subjects with poorly controlled hypertension during Study C-935788-047 or C-935788-048, defined as persistent or repeated systolic ≥ 140 mmHg, or diastolic ≥ 90 mmHg whether or not the subject is receiving antihypertensive treatment.
3. Subjects with the following laboratory abnormalities at the time of enrollment (Day 1): a leukocyte count $< 2,000/\mu\text{L}$, an ANC of $< 1,000/\mu\text{L}$, lymphocyte count $< 750/\mu\text{L}$, Hgb < 10 g/dL, or transaminase levels (ALT, AST) > 1.5 x ULN, bilirubin > 1.5 x ULN, or estimated glomerular filtration rate (eGFR) < 30 mL/min.
4. Subjects who have a significant infection, an acute infection such as influenza, or known inflammatory process at the time of enrollment into this study.
5. Subjects who have received any blood or blood products within the 2 weeks prior to enrollment (IVIg or anti-D are allowed if used for rescue therapy).

7.0 STUDY PROCEDURES

The study procedures to be performed at each visit are shown in [Table 2](#).

7.1 Treatment Period

7.1.1 Enrollment (Day 1)

Subjects must be willing to sign and date an Institutional Review Board (IRB)/Independent Ethics Committee (IEC) approved informed consent form (ICF) prior to participating in any study-specific procedure activities. Subjects will retain their same Subject ID number as per Study C-935788-047 or C-935788-048, as applicable.

Subjects who have completed the Week 24 assessments in the previous ITP study within 7 days of enrollment in the extension study do not need to repeat these same assessments. The assessments performed during the Week 24 visit in the prior ITP study will be used to qualify subject for enrollment in the extension study. The subject must sign the ICF prior to enrollment in the extension study. The following assessments must be performed in order for a subject to be eligible for the extension study.

All local and central laboratory results must be reviewed for eligibility prior to enrollment.

- Inclusion/Exclusion Criteria
- SF-36, (must be administered prior to any other study specific procedures (refer to [Appendix 5](#))
- Physical examination, vital signs, and KPS (refer to [Error! Reference source not found.](#))
- Concomitant medications
- Bleeding Assessments by ITP Bleeding Scale (IBLS) (refer to [Appendix 7](#))
- 12-lead electrocardiogram (ECG)
- Complete blood count (CBC) with differential and reticulocyte count
- Platelet count (performed at institutional or local lab)
- Serum chemistry
- Immunoglobulin levels
- Urinalysis
- Pregnancy test (for females of childbearing potential)
- AEs

Table 2: Schedule of Study Procedures

	Day 1 Screen/ Enrollment^a	End of Month 1 (± 3 days)	Months 2–18 (± 3 days)	Months 19–60 (± 1 week)	Follow-up (± 7 days)ⁱ
Informed consent	X				
Inclusion/Exclusion	X				
Physical exam/KPS	X	X	monthly	every other month	X
Concomitant medications	X	X	monthly	every other month	X
Vital signs ^b	X	X	monthly	every other month	X
Bleeding assessment ^c	X	X	monthly	every other month	X
ECG	X				
Hematology ^d	X		monthly	every other month	X
Platelets	X	X	monthly	every other month	X
Serum chemistries (including LFTs) ^e	X		Months 4, 8, 12, 16	every other month	X
LFTs only ^f			monthly (in months full serum chemistries not done)		X
Immunoglobulin levels	X				X
Urinalysis	X		Months 4, 8, 12, 16	every 4 months	X
Urine pregnancy test ^g	X		every other month	every other month	
SF-36 ^h	X		Month 12		
AEs	X	X	monthly	every other month	X
PK			Month 2		
Study drug dispensed/Accountability	X	X	monthly	every other month	
Dose adjustment (prn)	X	X	monthly	every other month	

a **Screen/Enrollment (Day 1):** These procedures are equivalent to Week 24 visit of Study C-935788-047 or C-935788-048; assessments performed as part of Week 24 may be used to assess subject's eligibility to roll over and do not need to be repeated specific to Study C-935788-049.

b **Vital Signs:** blood pressure, pulse and temperature

c **Bleeding assessment:** IBLS scale only; prior to Version 4, protocol used both IBLS (Appendix 7) and WHO (Appendix 8) bleeding scales

d **Hematology:** CBC with differential, RBC, hemoglobin, hematocrit, MCHC, MCH, MCV, MPV, RDW, reticulocytes

e **Serum chemistries:** Na, K, Cl, bicarbonate (CO₂), Ca, PO₄, BUN, creatinine, globulin, glucose, LDH, AST, ALT, alkaline phosphatase, total bilirubin, total protein, albumin

f **LFTs:** ALT, AST, ALP, LDH, and bilirubin (total and direct)

g **Pregnancy Test:** For women of childbearing potential, regardless of birth control methodology

h **SF-36:** At visits where the SF-36 is evaluated the SF-36 must be the first assessment performed.

i **Follow-up visit:** to be completed approximately 2 weeks (+/- 7 days) after subject's last treatment or at the time of early treatment termination

Baseline measurements will be the last measurement for the corresponding variable prior to the first randomized dose (Visit 3) in the C-935788-047 or C-935788-048 study.

Once a subject has been enrolled, a new bottle(s) of fostamatinib will be dispensed.

7.1.2 Treatment Visits

The treatment period begins at the time of enrollment and may continue up to a total of 60 months. Over the course of the study, subjects will be expected to visit the clinic monthly for the first 18 months, followed by every 2 months for the remainder of the study. Assessments including platelet counts will be performed to evaluate the safety and efficacy of fostamatinib, and to determine if a dose adjustment is required. All visits are determined by the date of enrollment and should occur within the windows specified (refer to Table 2 for the complete schedule of study procedures).

[figure not shown]
Study drug accountability will be performed at each visit. New bottle of fostamatinib will be dispensed using the IWRS at each visit. Used bottles will be returned for accountability. At the final visit of the treatment period, final study drug accountability will be performed.

7.2 Dose Adjustments

7.2.1 Dose Escalation for Subjects Not Responding at End of Month 1

The initial dose will be determined by a subject’s response to treatment in Study C-935788-047 or C-935788-048 (see Section 5.3). At the end of Month 1 (approximately Day 30), subjects who initiated dosing at fostamatinib 100 mg PO *bid* in the extension study (and who have not previously had a dose reduction) should have their dose increased to fostamatinib 150 mg PO *bid* if the platelet count remains below 50,000/ μ L and the study drug has been well tolerated (see Figure 3). All subjects whose dose is escalated should continue to be monitored carefully for AEs associated with fostamatinib treatment.

Figure 3: Dose Escalation (Subjects starting at 100 mg *bid* who have not Previously had a Dose Reduction)

The dose may be escalated beginning at Month 1 and any visit thereafter.

7.2.2 Dose Adjustments Due to Adverse Events

Treatment with fostamatinib has been associated with AEs that may require temporary interruption of the study drug and/or a reduction in study drug dose. Modification of study drug administration may be required under the following circumstances:

- Increases in ALT, AST, or bilirubin (refer to Appendix 1 for guidance regarding LFT-related dose adjustments)
- ANC $<1000/\text{mm}^3$ or $1.0 \times 10^9/\text{L}$ (refer to Appendix 2 for guidance regarding management of neutropenia)
- Severe diarrhea (refer to Appendix 3 for guidance regarding diarrhea-related dose adjustments) ⁽²⁾
- Increase in BP to $> 140/90$ mmHg (refer to Appendix 4 for guidance regarding BP-related dose adjustments)
- Other severe or life-threatening AEs considered related to study drug administration

Subjects who have their dose reduced may be considered for a re-escalation of the study drug dose, following resolution of the AE resulting in dose reduction, and only after consultation with the Medical Monitor. If a subject experiences additional dose-limiting AEs, the dose of study drug may be further reduced to a dose as low as 100 mg *qd*. When dose reduction results in a once-daily dose of fostamatinib, subjects will take the daily study drug dose in the morning.

Table 3 details the strategy for dose adjustment in subjects who experience AEs requiring dose reduction.

Table 3: Dose Adjustment

Dose	Dose Level -1	Dose Level -2	Dose Level -3a	Dose Level -4a
100 mg PO bid	150 mg PO qd	100 mg PO qd	discontinue	----
150 mg PO bid	100 mg PO bid	150 mg PO qd	100 mg PO qd	discontinue

a. The Sponsor's Medical Monitor should be consulted prior to consideration of dose modification to levels -3 or -4.

7.2.3 Non-Diarrhea Gastrointestinal Toxicity

Nausea, vomiting, and abdominal pain have been reported in association with fostamatinib treatment. Symptomatic treatment, (eg, omeprazole or ranitidine for gastric distress) should be initiated promptly. In the event of significant upper abdominal pain/distress, consideration should be given to the possibility of pancreatitis and serum amylase and lipase should be monitored.

7.3 Discontinuation of Nonresponders

After 3 months (12 weeks) of treatment, (and a minimum of 4 weeks treatment at 150 mg PO *bid*, unless this higher dose was not tolerated), any subject whose platelet count consistently

remains $< 50,000/\mu\text{L}$ should be discontinued from the study, unless tangible clinical benefit from the use of fostamatinib is evident and the Sponsor agrees (discuss any exceptions with the Sponsor's Medical Monitor). Examples of tangible clinical benefit may include, but are not limited to:

- Credible increase in platelet count (eg, increase in platelet count of at least $20,000/\mu\text{L}$ over the initial baseline to a count $\geq 30,000/\mu\text{L}$)
- Reduction in bleeding
- Reduction in the need for rescue therapy

7.4 Rescue Therapy

Certain therapeutic regimens for ITP will be permitted for subjects with platelet counts $< 50,000/\mu\text{L}$ who need “rescue” support of the platelet count.

Circumstances in which “rescue” therapy can be administered include:

- Platelet count $< 50,000/\mu\text{L}$ and at immediate risk of bleeding or with clinically significant bleeding or wet purpura
- Platelet count $< 50,000/\mu\text{L}$ and requires urgent or emergent surgery

Allowed therapeutic regimens include:

- IVIg: up to $1 \text{ g/kg} \times 1\text{-}3$ days, or
- IV anti-D: up to $50\text{-}75 \mu\text{g/kg} \times 1\text{-}2$ days, or
- IV methylprednisolone up to $1 \text{ g/day} \times 1\text{-}3$ days or oral dexamethasone up to $40 \text{ mg/day} \times 1\text{-}2$ days or oral prednisone up to $1 \text{ mg/kg/day} \times 1\text{-}3$ days

The Investigator must discuss all instances of “rescue therapy” with the Sponsor's Medical Monitor, in advance of initiating the therapy whenever possible.

7.5 Study Follow-Up

Subjects will be instructed to return to the clinic 2 weeks following the last dose of study drug for follow-up study assessments. If a SAE is present at the last visit, follow-up should occur as indicated in [Section 9.3](#).

7.6 Definition of Study Procedures

7.6.1 Physical Exam

The initial physical exam should include evaluation of the head, eye, ear, nose, and throat, cardiovascular, dermatological, musculoskeletal, respiratory, gastrointestinal, and neurological systems as well as an assessment of the Karnofsky Performance Status (Appendix 6). Physical examinations will include weight at the enrollment visit only. Subsequent examinations may be symptom-directed at the discretion of the Investigator. Physical examinations will be performed

as per the study schedule in Table 2. Any new or worsened abnormalities should be recorded as AEs after enrollment. No rectal or pelvic examination is required.

7.6.2 Karnofsky Performance Status Assessment

The KPS ⁽³⁾ is a widely used method used to assess the functional status of patients. KPS will be collected as part of the eligibility criteria. The KPS describes the patient's functional status using percentage value ranges from 100%, no evidence of disease to 0%, death. The assessor must also be the same person who is performing the physical exam for the study visit.

7.6.3 Vital Signs

Vital signs (including blood pressure, pulse, and temperature) will be assessed at each study visit. All blood pressure determinations should be made with the subject seated and taken after the subject rests for 3 minutes. If the initial blood pressure at any visit is > 130 mmHg systolic or > 80 mmHg diastolic, the blood pressure should be taken at least 2 additional times at least 5-10 minutes apart, and all 3 measurements will be recorded in the eCRF.

7.6.4 Bleeding Assessment

Bleeding symptoms will be assessed using the IBLS at each study visit. ⁽⁴⁾ The IBLS will include assessment of bleeding at 9 anatomical sites over the past week graded from 0 (none) to 2 (marked bleeding). Assessment of bleeding at 2 sites, skin and oral, should be assessed by physical examination (see Appendix 7).

The World Health Organization bleeding scale (Appendix 8) was collected during the first 2 years of treatment, but has been discontinued in Version 4 of the protocol.

The assessor must be a physician, doctor of osteopathic medicine, physician's assistant, or nurse practitioner. The assessor must also be the same person who is performing the physical exam for the study visit. The IBLS is to be performed by the same assessor for each subject at each study visit, whenever possible.

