#### 4.5. Safety Endpoints

The following safety endpoints will be evaluated:

- Adverse events
- Adverse events of interest, including:

- Gastrointestinal (GI) events
  - Nausea
  - Vomiting,
  - Diarrhea as reported by SMQ (v19.1) of non-infectious diarrhea
  - Abdominal pain
- Infection
- Hypertension as reported by SMQ (v19.1)
- Increases in transaminases and/or total bilirubin as defined by SMQ (v19.1) of Hepatic Disorder
- Neutropenia
- Percent change from baseline in lab assessments (hematology, serum chemistry and liver function tests) over time
- Presence of abnormal changes from baseline in laboratory values per Common Terminology Criteria for Adverse Events (CTCAE) criteria V 5.0 (e.g., hematology, chemistry)
- Severity of bleeding according to the IBLS and the WHO bleeding scale
- Change from baseline in vital signs (i.e., systolic /diastolic blood pressures, pulse, temperature) over time
- Post baseline blood pressure categorized based on post baseline systolic and diastolic blood pressure values.

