### 11.1 Adverse Events

Analyses of adverse events (AEs) will include all adverse events in the present study, not just treatment emergent AEs (e.g., if a placebo patient has an AE starting in C-935788-047/C-935788-048 studies and continuing in the present study, this AE will be included in the analyses) . Adverse events will be coded using the Medical Dictionary for Regulatory Activities (MedDRA 19.1). The number of events and the number and percentage of patients with at least 1 adverse event, at least one severe AE, at least one moderate or severe AE, at least 1 serious adverse event (SAE), at least 1 treatment related adverse event, at least one adverse event leading to dose reduction, at least one adverse event leading to dose interruption, at least one adverse event leading to drug withdrawal, and at least one adverse event leading to death will be presented. AEs that are possibly or probably related to study treatment, or for which the relationship to study treatment is missing, will be considered treatment related. Among patients with at least one AE, the mean number of AEs per patient will also be presented. The number and percentage of patients with adverse events of interest [any gastrointestinal (GI) complaints (nausea, vomiting, diarrhea, abdominal pain), overall and separately, infection, hypertension, neutropenia, transaminase elevation, and bilirubin elevation] will be presented. For the AEs of nausea, vomiting, abdominal pain, and infection, Rigel will specify preferred terms that fit into these categories. AEs, SAEs, AEs of interest, AEs leading to dose reduction, AEs leading to dose interruption, AEs leading to drug withdrawal, and AEs leading to death will be summarized at the patient level by MedDRA system organ class (SOC) and preferred term using frequencies and percentages. AEs will also be tabulated at the event level and the patient level by severity

and by causal relationship to study drug. AEs of interest will be tabulated at the event level and the patient level by severity.

Regarding diarrhea (as reported by SMQ 19.1), the following additional analyses will be performed:

- A patient's maximum diarrhea severity grade for the post-baseline period will be summarized using counts and percentages.
- A patient level of listing for diarrhea that include the diarrhea severity grade, diarrhea start and end dates and duration of diarrhea in the present study will be provided.

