#### **11.4 IBLS and WHO Bleeding Scale Scores**

The IBLS will be analyzed as follows:

- The mean of the IBLS scores across 9 anatomical sites and across visits during the 24-month treatment period in present study will be summarized using descriptive statistics.
- The highest IBLS score across the 9 anatomical sites and the total IBLS score will be summarized by visit.

The WHO bleeding scale will be analyzed as follows:

- The mean of the WHO bleeding scale across visits during the 24-month treatment period in present study will be summarized using descriptive statistics.

In addition, both IBLS bleeding scale and WHO bleeding scale analyses mentioned above will be performed by prior study treatment group and overall.

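### Bleeding frequency is a protocol safety endpoint, but the IBLS recalls only the past week at visits one and then two months apart, and no pooled bleeding adverse event summary is planned to fill the gap

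*Protocol*

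**What the plan says.** **Endpoint.** Protocol 4.4 begins "Safety endpoints include the frequency and severity of bleeding" and names the IBLS as the measure. Protocol 10.5 repeats the endpoint, but the only IBLS analysis it plans is the mean score over visits.

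**Instrument.** Protocol 7.6.4 states: "The IBLS will include assessment of bleeding at 9 anatomical sites over the past week graded from 0 (none) to 2 (marked bleeding"). Skin and mouth are also scored by physical examination at the visit. The WHO scale was used alongside the IBLS until protocol Version 4. Neither Protocol 7.6.4 nor Appendix 8 gives it a recall period.

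**Visits.** Protocol 7.1.2 schedules clinic visits "monthly for the first 18 months, followed by every 2 months for the remainder of the study". The schedule table ties the bleeding assessment to those visits.

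**SAP endpoint and analysis.** SAP 4.5 lists "Severity of bleeding according to the IBLS and the WHO bleeding scale"; frequency is absent. SAP 3.5, which records departures from the protocol analyses, does not mention this. SAP 11.4 plans the mean IBLS over the nine sites and "across visits during the 24-month treatment period in present study will be summarized using descriptive statistics", plus the highest and total score by visit. A mean is planned for the WHO scale.

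**Adverse events.** Under Protocol 9.2.1 the reporting period runs without a break from the last dose in the prior study to the Follow-Up visit. Protocol 9.1 counts new signs or symptoms of the target disease, and worsening of pre-existing conditions. SAP 11.1 tabulates all adverse events by patient, by system organ class and preferred term. Its adverse events of interest are gastrointestinal complaints, "overall and separately, infection, hypertension, neutropenia, transaminase elevation, and bilirubin elevation". Bleeding is not among them.

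**The concern.** Long-term safety is the primary objective, and Protocol 3.1 identifies haemorrhage as the risk that severely thrombocytopenic patients carry. A reader of the study report will ask how many patients bled, how often, and how seriously. The IBLS outputs answer a different question: how much bleeding was present or recalled in the week before each visit. An episode that ended earlier than that does not enter the score.

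The continuously collected adverse event data could answer the question, but the visible plan leaves them as separate preferred-term rows. The frequency half of the protocol endpoint then has no planned analysis and no recorded reason for its removal. Bleeding also bears on decisions in the study: Protocol 5.3 and 7.3 give a reduction in bleeding as one example of benefit that may support continued treatment of a nonresponder.

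**Working it through.** The documents state no coverage figure, so there is none to reproduce.

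**Inputs**
- Recall: 7 days (Protocol 7.6.4).
- Visit interval: 1 month to Month 18, then 2 months to Month 60 (Protocol 7.1.2).
- Length of a month: 365.25/12 = 30.44 days.
- Day 1 and Follow-up are not counted, because their recall does not fall wholly within treatment in this study.

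**Step 1. Share of time outside IBLS recall, 1 − 7/interval**
- Monthly: 7/30.44 = 23.0% covered, 77.0% outside.
- Two-monthly: 7/60.88 = 11.5% covered, 88.5% outside.

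**Step 2. Average over a course, 1 − 7 × visits/days**
- 24 months: 18 + 3 = 21 visits; 21 × 7 = 147 of 730.5 days; 79.9% outside.
- 60 months: 18 + 21 = 39 visits; 39 × 7 = 273 of 1,826 days; 85.1% outside.

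**Step 3. Effect of the 24-month limit on the mean.** For a patient treated for 60 months, the mean in SAP 11.4 uses 21 of 39 visits. Those windows cover 147 of 1,826 days, so 92.0% of treatment time contributes nothing to the mean. The by-visit summaries carry no such limit.

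**Step 4. Visit windows.** A 28-day interval leaves 75% outside. A two-month interval stretched by one week at each end (74.9 days) leaves 90.7% outside. Visits are timed from enrolment, so these shifts hardly alter the averages in Step 2.

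**Step 5. Chance that one episode is seen.** For a bleed of d days starting at random, the chance of touching a recall window is (6 + d)/interval.

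| Duration | Monthly | Two-monthly |
|---|---|---|
| 1 day | 7/30.44 = 23% | 7/60.88 = 11.5% |
| 3 days | 9/30.44 = 30% | 9/60.88 = 15% |
| 5 days | 11/30.44 = 36% | 11/60.88 = 18% |

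This assumes that bleeding does not prompt an unscheduled IBLS.

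**Step 6. Can the adverse event tables supply the missing count?** Not as planned. The IBLS sites range over skin, mouth, nose, gut, urinary and gynaecological tract, lung, brain and eye, so bleeding terms will be spread over several body systems. If two terms affect a and b of N patients, the number with either lies anywhere from max(a, b) to min(a + b, N), and the rows do not say where. The pilot data in Protocol 3.3 show that such terms do get reported: petechiae in 10 of 18 patients in the initial period, and ecchymosis in 9 of 13 in the extension period. The summary there gives no figure for any bleeding.

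**The case against.** The strongest reply is that little is lost. Bleeding between visits is reportable throughout, every bleeding term gets a patient count, and adverse events are also tabulated by severity and causality. The missing piece is a grouping of rows that could be produced at any time. This is right about the data. It does not answer the point about the plan: a grouping chosen after the data are seen is weaker than one fixed beforehand, and the frequency half of the endpoint remains without an analysis.

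Four stronger readings are tempting, and the documents do not support them.

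- **A reader might infer that 77% to 88.5% of treatment time escapes all bleeding analysis.** It escapes IBLS recall only. Adverse event reporting covers the whole period.
- **A reader might infer that bleeding adverse events are never counted per patient.** SAP 11.1 counts patients for each preferred term. What is absent is a count across terms.
- **A reader might infer that the wider spacing after Month 18 could produce an apparent late fall in bleeding.** The window is the same 7 days at every visit, so the expected score does not depend on the gap before it. Wider spacing costs precision. It would lower a cumulative count of IBLS-positive episodes, but none is planned.
- **A reader might apply the percentages to the WHO scale.** That scale has no stated recall period, so they cannot be carried over.

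Two limits also stand. Rescue therapy is summarised in SAP 12.5 and may be given for clinically significant bleeding, but it is also allowed for immediate bleeding risk and for urgent surgery, so it is not a bleeding count. The items in SAP Appendix 14.1 are redacted and one might concern bleeding, so the finding applies to the visible plan.

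**Conclusion.** The concern holds in a limited form. IBLS recall covers about 23% of treatment time with monthly visits and 11.5% with two-monthly visits, or about 15% over a full 60 months. The SAP reduces the protocol endpoint from frequency and severity to severity alone without recording the change, and it confines the mean IBLS to 24 months of a treatment period that may last 60. Bleeding outside the recall windows is collected and listed by term but never pooled. The visible plan therefore yields neither the number of patients with any bleeding nor an event rate.

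The percentages assume full attendance and a strict 7-day recall for every history item. The 60-month figures are a far limit, since treatment stops earlier if the drug becomes commercially available. Unsampled time does not bias the IBLS scores in itself; what the scores cannot give is incidence. The gap is one of analysis and labelling, cheap to close, and worth closing because bleeding is central to the primary safety objective.

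**What to change.** 1. Add bleeding to the adverse events of interest in SAP 4.5 and 11.1. Define it by a MedDRA 19.1 haemorrhage SMQ or by a prespecified list of preferred terms. The SAP already uses SMQs for diarrhea, hypertension and hepatic events, and sponsor-specified terms for other categories.
2. Report how many patients, and what percentage, had any bleeding event, a moderate or severe one, and a serious one, together with events per patient-year. Name this as the measure of bleeding frequency.
3. Label all IBLS results as bleeding in the 7 days before each visit.
4. Record in SAP 3.5 how the frequency part of the endpoint is now handled. State there too whether the 24-month limit on the mean IBLS is intended.

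The cost is SAP wording and one more table from data already collected and coded, with exposure taken from the dosing duration in SAP 9.0. The downside should be stated beside the table: adverse event capture depends on what patients mention and sites record, and under Protocol 9.1 pre-existing bleeding counts only if it worsens, so the pooled figure may understate total bleeding.
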